PROTOCOL SUMMARY

TITLE OF THE STUDY: MERIT: Beta Adrenergic Antagonist For The Healing of Chronic Diabetic Foot Ulcers

Start Date: 04/01/2017
Ending Date 12/31/2024

PHASE: 2

METHODOLOGY: It is a prospective, randomized, double blinded, controlled, and parallel-group study with 2 arms. Follow up cohort will include a real-world group.

STUDY DURATION: 31 weeks

TREATMENT PHASE: 12 weeks

FOLLOW-UP PHASE: 16 weeks

REAL-WORLD GROUP: 12 weeks

STUDY CENTERS: One centralized study location Multispecialty Wound Healing Clinic at Sacramento VA Medical Center.

Note: Primary Care, Vascular, Podiatry and Dermatology clinics from the at the Veteran Affairs Northern California Health Care System (VANCHS) satellite clinics (Redding, Chico, Martinez, Oakland, McClellan, and Fairfield) will refer patients to the study location.

NUMBER OF SUBJECTS: 2 treatment arms, 24 subjects per arm for a total of 48; Screen-failed patients to be followed passively on the status of their diabetic foot ulcer via CPRS. Additional patients will be screened and enrolled for exploratory follow up to study inflammatory markers in non-healing patients.

STUDY OBJECTIVES: The primary objective of this study is to assess the effectiveness of the topically applied Timoptic-XE® or timolol (a non-selective beta adrenergic receptor antagonist (β BAR)) versus standard of care for the treatment of non-healing diabetic foot ulcers. The primary endpoint will be the measurement of the complete ulcer closure (as defined by “skin re-epithelialization without drainage or dressing requirements) at 12 weeks. The secondary outcomes will be the following: comparison of percent difference change in size from the randomization visit to the endpoint visit (post 12 weeks) between the treatment and control group, the time to wound closure between the two groups, and wound healing rates with impact of wound size between the treatment groups, change in trans-epidermal water loss measurements at sites of healed wounds, measurement of quality of life using Veterans Rand (VR-36) Health Survey, measurement of the Lower Extremity Functional Scale Outcome and the Charlson Comorbidity Index.

The secondary objective of study is to profile the safety of topically applied Timoptic- XE® in the treatment of DFU. We will monitor serum levels of timolol post-application to determine the plasma concentration of timolol in relation to its systemic bioavailability. Timolol levels will be determined using reversed-phase ultraperformance liquid chromatography and UV detection. The primary safety outcome will be the measurement of timolol serum during the treatment phase.

The secondary safety outcomes will be the following: the mean changes from baseline in systolic and diastolic blood pressure in mmHg, the mean changes from baseline in heart rate in beats per minute, and the measurement of all the adverse events associated with the use of Timoptic-XE®.

INCLUSION CRITERIA:

1. Male or female subject of any race 18 years old or older
2. Lower extremity ulcer located anywhere on the foot up to the ankle:
 - a. Of more than 30 days duration and less than 2 years duration (medically documented)
 - b. Surface area between 0.5cm² and 20cm² (as measured with the Silhouette imaging system at randomization). The ulcer with largest surface area meeting inclusion criteria will be selected as index ulcer
 - c. If two ulcers present with the same surface area, the ulcer of the longest duration will be selected as index ulcer
3. Documented Ankle Brachial Index (ABI) between 0.8 and 1.2 on the study limb or toe pressure over 65mmHg within 3 months of screening phase
4. Documented biopsy report to rule out malignancy of ulcer of > 6 months duration

EXCLUSION CRITERIA*:

A subject will be excluded from the study if any of the following criteria are met:

1. Ulcer of non-diabetic etiology, such as venous, arterial and burn wounds
2. Index ulcer is less than 3 cm in distance from any other ulcer on the same extremity
3. There are greater than 3 ulcers on the study foot
4. Index ulcer presents with any of the following: cellulitis, osteomyelitis, exposed bone, tendon or fascia, purulent exudate or gangrene
5. Index ulcer shows evidence of infection (defined as a moderate or severe rating of all of the following clinical signs/symptoms: 1) increased warmth, 2) increased pain, 3) erythema, and 4) malodorous exudate at Screening or at Randomization (Visit 1), OR total organism count > 1 x 10⁵ colony forming units (CFU) from the screening visit study ulcer culture sample)
6. Index ulcer surface area has decreased or increased > 40% between Screening and at Randomization (Visit 1) as assessed by the Silhouette imaging system
7. Has medically documented history of Human Immunodeficiency Virus (HIV)
8. Has active malignancy on the study limb
9. Has uncontrolled diabetes mellitus as defined by glycosylated hemoglobin A1C > 12% within 3 months of screening
10. Has immunodeficiency as defined by serum IgG, IgA, and IgM less than one-half the lower limit of normal
11. Has severe protein malnutrition as defined by serum albumin < 2.5 g/dL

12. Has serum aspartate aminotransferase (AST, SGOT, GOT) or serum alanine aminotransferase (ALT, SGPT, GPT) levels greater than twice the upper limit of normal
13. Has fatigue, palpitations, dyspnea, and/or angina at rest
14. Has a medically documented or self-reported history, within the previous 12 months from date of Screening Visit, of alcohol or drug abuse, particularly methadone or heroin
15. Has received previous treatment with the following during the 60 days prior to Screening: Immunosuppressive agents, radiation, chemotherapy, growth factors (epidermal growth factor, tumor necrosis factor, transforming growth factor, platelet derived growth factor, etc.)
16. Has received previous treatment with the following during the 30 days prior to screening: the site of the study ulcer, split- or full-thickness skin graft at the site of the study ulcer, biologically-active (or engineered) cellular or acellular product(s) at the site of the study ulcer, investigational drug or device
17. Has been hospitalized for treatment of a diabetic foot ulcer within the previous 30 days from Screening
18. Has history of bradycardia (heart rate less than 60)
19. Has ESR>70mm/hr and CRP>100 mg/L at time of screening
20. Has medically documented history of hypotension/orthostatic hypotension and/or symptomatic hypotension (systolic blood pressure below 90 and diastolic blood pressure less than 60). (Note: There is no standard testing regimen protocol for orthostatic hypotension, even for patients starting on oral timolol, per the consultant Cardiologist, [name])
21. Currently taking asthma or COPD medications (as documented in chart)
22. Has a medically documented diagnosis of myasthenia gravis, untreated hyperthyroidism, , Type 2, Type 3 heart block, cardiogenic shock, overt cardiac failure
23. Female who is pregnant or refuses to use adequate contraceptive methods and is of childbearing age during the trial
24. Prisoners, institutionalized individuals or vulnerable population
(The real-world group will not have any exclusion criteria related to timolol (criteria 18-22)

(*)Note: The exclusion criteria were modified compared to the original submission based on the recommendation from the DMC, which suggested that these criteria would significantly impair the enrollment. Those were also revised upon evaluation by the consultant Cardiologist, [name].

TREATMENT: Total duration of study per subject: Up to 31 weeks (Includes to 2 weeks of screening and up to 16 weeks until the end of the follow-up period). 12 weeks for the real-world group.

DURATION OF ADMINISTRATION: Daily application for 12 weeks (starting at Visit 3/Week 3).

STUDY DESIGN: This is a prospective, randomized, double blinded, controlled, and parallel-group study with 2 arms: β AR antagonist (SOC plus topically applied Timoptic-XE®) and control (standard of care (SOC) plus non-biologically active gel (hydrogel, Kendall®, placebo medication)).

EFFICACY ENDPOINTS:**PRIMARY EFFICACY OUTCOME**

1. Complete closure of ulcer by Visit 14/Week 14

SECONDARY EFFICACY OUTCOME

1. Complete closure of ulcer by Week 31
2. Percent difference change in size from the randomization visit to the endpoint visit (post 12 weeks)
3. Time to wound closure
4. Rate of ulcer healing
5. Change in transepidermal water loss of re-epithelialized wound after wound closure

SAFETY ENDPOINT:**PRIMARY SAFETY OUTCOME**

1. Timolol serum levels during the treatment phase

SECONDARY SAFETY OUTCOME

1. Mean changes from baseline in systolic and diastolic blood pressure in mmHg
2. Mean changes from baseline in heart rate in beats per minute
3. Adverse events associated with the use of timolol.

QUALITY OF LIFE ASSESSMENT: We will use ANCOVA to analyze the quality of life from the VR-36 Health Survey and the Lower Extremity Functional Scale Outcome Questionnaire.

DATA ANALYSIS:

The primary outcome is complete ulcer closure by Week 12 (end of the Active Phase) of the study and the rate of ulcer healing by the 12th week of care between the two arms.

Hypothesis to be tested: The null hypothesis is that there is no difference in the proportion of subjects with complete wound closure of DFU between the timolol treatment group and the control group. Complete wound closure is defined as 100% closure, or skin re-epithelialization without any drainage present or dressing requirements. Two-sided Fisher's exact test will be used to compare the proportion of complete ulcer closure by Week 12 (end of the Active Phase) of the study and the rate of ulcer healing by the 12th week of care between the two arms. The Kaplan-Meier method will be used to estimate the survival function of time to achieve complete ulcer closure (if less than 12 weeks) for each arm, and a two-sided log-rank test will be used to compare the survival curves between the two arms.

The area of the target ulcer will be summarized by treatment group and visit. Both actual value and change from the previous visits ulcer area will be presented. A second summary of target ulcer area will also be given which will present change from baseline. The weekly change and the percentage weekly change in the target ulcer area from visit to visit will be summarized by treatment group and visit. The two-sided t-test or Wilcoxon rank-sum test as appropriate will be used to compare relative ulcer area from baseline to Week 12 between the two arms.

Chi-square test or Fisher's exact test as appropriate will be used to compare wound healing rates in relationship to wound size, as well as wound healing rates between the treatment groups at the 4-week follow-up and at the 12-week follow-up period and recidivism rate.

Additional secondary analyses to evaluate the association of specific wound characteristics (such as wound size, wound location) and subject characteristics (body mass index, chronicity of the wound, history of DVT, length of diabetes, HbA1c, and ABI/toe pressure will be conducted using logistic regression. Further logistic regression will be used to investigate the relationship between the occurrence of each type of adverse event and treatment in order to adjust for each of the potential confounding factors previously listed.

A two-way ANOVA with a post hoc test will be used to determine the relationship between timolol serum levels and wound healing.

Further statistical analysis will be used to determine the relationship between serum inflammatory markers and wound healing.

For demographic and clinical characteristic data at baseline, continuous variables will be summarized (when appropriate) by using mean, median, standard deviation, co-efficient of variation, minimum value and maximum value. Categorical variables will be summarized with frequency tables. Baseline comparability between the two treatment groups will be assessed by using the independent two-sample t-test or Wilcoxon rank-sum test and the Chi-square test or Fisher's exact test.

Following wound closure, comparison of changes in the epidermal barrier function of healed ulcers treated with timolol vs those treated with saline control will be non-invasively measured quantitating the transepidermal water loss (TEWL). Categorical variables will be summarized with frequency tables. Baseline comparability between the two treatment groups will be assessed by using the independent two-sample t-test or Wilcoxon rank-sum test and the Chi-square test or Fisher's exact test.

TABLE OF CONTENTS

- 1 BACKGROUND AND RATIONALE
- 2 OBJECTIVES
- 3 STUDY POPULATION
- 4 STUDY PROCEDURES
 - 4.1 DESIGN AND METHODOLOGY
 - 4.2 DESCRIPTION OF STUDY GROUPS
 - 4.3 STUDY FLOW CHART
 - 4.3.1 SCREENING/BASELINE PERIOD (VISIT 1 to 2/WEEKS 1 to 2)
 - 4.3.2 RANDOMIZATION (VISIT 3/WEEK 3)
 - 4.3.3 TREATMENT PHASE (VISIT 4/WEEK 4)
 - TREATMENT PHASE (VISIT 5/WEEK 5)
 - TREATMENT PHASE (VISIT 6/WEEK 6)
 - TREATMENT PHASE (VISIT 7/WEEK 7)
 - TREATMENT PHASE (VISIT 8/WEEK 8)
 - TREATMENT PHASE (VISIT 9/WEEK 9)
 - TREATMENT PHASE (VISIT 10/WEEK 10)
 - TREATMENT PHASE (VISIT 11/WEEK 11)
 - TREATMENT PHASE (VISIT 12/WEEK 12)
 - TREATMENT PHASE (VISIT 13/WEEK 13)
 - TREATMENT PHASE (VISIT 14/WEEK 14)
 - 4.3.4 STUDY ENDPOINT (VISIT 14/WEEK 14)
 - 4.3.5 2ND CONFIRMATORY VISIT (VISIT 15/WEEK 15)
 - 4.3.6 FOLLOW-UP PHASE (VISIT 16/WEEK 19)
 - FOLLOW-UP PHASE (VISIT 17/WEEK 23)
 - FOLLOW-UP PHASE (VISIT 18/WEEK 27)
 - FOLLOW-UP PHASE (VISIT 19/WEEK 31)
 - 4.3.7. REAL-WORLD GROUP PHASES
 - SCREENING/BASELINE PERIOD (VISIT 1/WEEK1)
 - FOLLOW-UP PHASE (VISIT 2/WEEK 6)
 - STUDY ENDPOINT (VISIT 3/WEEK12)
 - 5 ADVERSE EVENTS
 - 6 STATISTICAL DESIGN
 - 7 APPENDIX 1 – Wound scoring system
 - 8 APPENDIX 2 – Hemostasis procedure
 - 9 APPENDIX 3 – Infection exclusion procedure
 - 10 APPENDIX 4 – Home Care Instructions

- 11 APPENDIX 5 – Veterans Rand-36 (VR-36) Health Survey**
- 12 APPENDIX 6 – Lower Extremity Functional Scale**
- 13 APPENDIX 7 – Charlson Comorbidity Index**

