1.1. STUDY FLOW CHART

Study Plan Schematic

Procedure	Screening Phase Visits 1-2 (Week 1-2)		Active Phase Visits 3-14 (Week 3-14) Including a 1st confirmatory visit if healed before 12 weeks of treatment		2nd Confirmatory Visit Prior to Follow-up Phase Visit 15 (Week 15)	Follow-up Phase Visits 16, 17, 18 & 19 (Week 19, 23, 27 & 31)			
	Visit 1 (Week 1)	Visit 2 (Week 2)	Visit 3 (Week 3) Randomization	Visits 4-14 (Week 4-14) Study Endpoint at Week 14*	Visit 15 (Week 15)	Visit 16 (Week 19)	Visit 17 (Week 23)	Visit 18 (Week 27)	Visit 19 (Week 31)
Inclusion/Exclusion Criteria	X	X	X						
Informed Consent/HIPAA document	X								

VR-36 Health Survey Questionnaire	X			X*					
Lower Extremity Functional Scale Outcome Questionnaire	X	X		X					X
Charlson-Comorbidity Index	X								
Physical Exam	X			X*					
EKG	X			X*					
Vital Signs	X	X	X	X	X	X	X	X	X
Ankle-Brachial Index/Duplex Scan	X	X							
Debrided Tissue for genetic analysis (Weeks,1-9)	X	X	X	X					
Bacterial, Fungal Infection and Malignancy Evaluation	X								
Laboratory evaluation (hematology, renal, and liver function)	X								
Vapometer Readings@ (@If healed, readings recorded from point of closure + 4 months)				X@	X	X	X	X	X
Blood Sample for Timolol assay/Inflammatory markers(weeks 4,8,12)	X			X†					
Ulcer Assessment	X	X	X	X	X	X	X	X	X
Debridement († if needed)	X	X	X	X	X†	X†	X†	X†	X†
Ulcer Photography and Area Measurement	X	X	X	X	X	X	X	X	X
Offloading device	X	X	X	X	X	X	X	X	X
Randomization			X						
SOC + Timoptic-XE@ or SOC + non biologically active gel (hydrogel as placebo medication)			X	X					

SOC			X	X	X	X	X	X	X
Concomitant Medications and Adverse Events	X	X	X	X	X	X	X	X	X

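### Heart rate and blood pressure are reported only as mean change, the EKG is not analysed, and no rule says when a measured value counts as an adverse event

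*Combined protocol and SAP*

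**What the plan says.** **Which harms the plan links to the drug.** Among the exclusions in the Protocol Summary, item 18 reads "Has history of bradycardia (heart rate less than 60". Item 20 covers documented hypotension, with the values "systolic blood pressure below 90 and diastolic blood pressure less than 60". Item 22 includes heart block. The note after item 24 makes the link explicit: "The real-world group will not have any exclusion criteria related to timolol (criteria 18-22".

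**What is measured.** The Study Flow Chart has vital signs at every visit. It has an EKG at Visit 1 and, through an asterisk tied to "Study Endpoint at Week 14", at the end of treatment. The Visit 14 list in Section 4.3.4 does not include the EKG.

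**What is reported.** The secondary safety outcomes are "Mean changes from baseline in systolic and diastolic blood pressure in mmHg", "Mean changes from baseline in heart rate in beats per minute" and "Adverse events associated with the use of timolol". Neither the Data Analysis part of the summary nor Section 6 gives heart rate or blood pressure a baseline definition, a visit, a between-arm contrast, a lowest value, a count or a listing. The EKG is in no outcome and no analysis.

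**Adverse events.** Section 5 records events found by report, questioning or investigator observation, and has them graded and attributed. Section 6 models each type of event on treatment by logistic regression. No section connects a measured heart rate, blood pressure or EKG finding to this process.

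**The concern.** The cardiovascular concerns the plan names are events in individual subjects: a low rate, a low pressure, a conduction block. An arm mean answers a different question, namely whether the average subject shifted. With about 24 subjects per arm, a large change confined to a few is diluted into a small average. As written, the mean is not even contrasted with the control arm.

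The adverse event route covers what someone notices and records. It does not reliably cover a low weekly reading without symptoms, or an EKG change nobody classes as an event. Profiling safety is the trial's second stated objective. The risk is a report that shows a small mean change and says nothing about such subjects, although the readings were taken.

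**Working it through.** **1. The plan's own figure.** Section 6 gives 24 subjects per arm for 80% power at 20% versus 63% healed, two-sided Fisher's exact test at 5%. Exact enumeration gives 79.5% at 23 per arm and 82.5% at 24, so 24 is reproduced and serves as the denominator. The documents give no figure for heart rate, blood pressure or EKG; the fall sizes and SDs below are assumptions.

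**2. Dilution.** If k of 24 subjects fall by D and the others do not change on average, the arm mean shifts by k × D / 24.
- 4 × 20 / 24 = 3.3 bpm
- 3 × 20 / 24 = 2.5 bpm
- 3 × 30 / 24 = 3.75 bpm
- 1 × 40 / 24 = 1.7 bpm

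This step needs no SD.

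**3. Visibility in a between-arm comparison of means.** Assume an SD of change of 8-12 bpm. The standard error of the difference is SD × √(2/24), which is 2.31 at SD 8 and 3.46 at SD 12. The 95% half-width is 1.96 times that, or 4.5 to 6.8 bpm, wider than any shift in step 2. In simulated trials (24 per arm, normal changes, k timolol subjects shifted down by 20 bpm), a two-sided t-test reaches p < 0.05 in 11-17% for k = 4 and 8-11% for k = 3.

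**4. What a count would show.** 4/24 = 16.7%, exact 95% CI 4.7% to 37.4%. Against 0/24 in control, 4 gives Fisher p = 0.11; 5 versus 0 is needed to reach p < 0.05 (p = 0.0496). With 0/24 observed, the upper limit (97.5% one-sided) is still 14.2%. Counts therefore make subjects visible but do not provide a powered test.

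**5. Low readings without any drug effect.** Assume a mean heart rate of 72-80 bpm, a between-subject SD of 8-10, an SD of change of 8-12 (SD of one reading = that / √2), a baseline reading of at least 60, and 11 independent weekly readings (Visits 4-14). Simulation then gives 9-50% of subjects with at least one reading below 60. That is 24 × 0.09 ≈ 2 to 24 × 0.50 = 12 subjects per arm. A one-arm count is uninterpretable; only the contrast between arms is informative.

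**6. Whether the adverse event regression closes the gap.** It is to adjust for eight listed factors: wound size, wound location, body mass index, wound chronicity, DVT history, length of diabetes, HbA1c and ABI/toe pressure. With 4 events against 0, the treatment odds ratio has no finite maximum-likelihood estimate, adjusted or not. With 1-3 events in 48 subjects, any estimate is unstable.

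**The case against.** The strongest reply is that adverse events stand directly below the two mean-change outcomes as the third secondary safety outcome. They include anything the investigator observes, and each type is compared between arms. Section 5 also provides for a cardiologist to help with blood pressure and pulse, a data monitoring committee, and review of emerging safety data. This stands. A reader might infer that serious falls vanish from the report, or that a new conduction block would never be reported; the documents do not support that.

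Three other inferences should be resisted:
- **That the exclusion values are on-treatment limits.** Items 18 and 20 are eligibility criteria about history, and item 20 joins systolic and diastolic with *and*. Nor does a 20 bpm fall necessarily cross 60: it does so only from a baseline below 80.
- **That screening out low values biases the mean change through regression to the mean.** This needs selection on the measured baseline reading, which these history-based items do not clearly impose. Any such effect would be shared by the randomised arms.
- **That a count alone reveals harm.** Step 5 shows that it can be swamped by ordinary variation.

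What survives is the missing link between measured values and adverse event recording. The outcome's wording, "Adverse events associated with the use of timolol", can also be read as depending on attribution. In addition, the Withdrawal text in Section 3 follows treated subjects to the end of the study, while Section 6 withdraws subjects with adverse events. Under withdrawal, affected subjects could drop out of later means.

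**Conclusion.** The point holds in a limited form. Symptomatic, observed or serious cardiovascular events should reach the report as adverse events. Asymptomatic low readings and EKG changes in a few subjects may not, because the only stated summary of the vital signs is a mean without a between-arm contrast, the EKG has no analysis, and no rule converts a measurement into an adverse event.

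For size, the illustration is 4 of 24 subjects falling by 20 bpm: a mean shift of 3.3 bpm, detected with 11-17% power. The power range rests on the assumed SD of 8-12 bpm and normal changes. The dilution is arithmetic, and the gap in the text depends on neither. The primary efficacy analysis is unaffected; what is only partly served is the safety objective. The sponsor should make the change.

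**What to change.** Add to the safety outcomes in the Protocol Summary and to Section 6, keeping the mean change:

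1. Report heart-rate and blood-pressure change as a between-arm difference with 95% CI, adjusted for the pre-treatment value (the average of Visits 1-3, with the Visit 3 reading taken before the first application).
2. By arm, show each subject's lowest treatment-phase value and largest fall. Give counts with exact 95% CIs in descriptive categories taken from the exclusion values: heart rate below 60; systolic below 90 jointly with diastolic below 60; and each pressure component separately. State that these are reporting categories, not clinical action limits, and that they are read only as a between-arm comparison.
3. Add a by-arm EKG shift table, Visit 1 to Week 14, marking whether the subject was still applying product, since application stops on healing.
4. State how measured heart rate, blood pressure and EKG findings map to adverse event recording. The rule itself is for the sponsor and its clinicians.

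Two sets of passages must be reconciled: the Study Flow Chart and Section 4.3.4 on the Week 14 EKG, and Section 3 (Withdrawal) and Section 6 on follow-up versus withdrawal after an adverse event.

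The cost is a paragraph of text and a few descriptive tables. Items 1 to 3 need no new visits or tests. The downside is more output that is not powered for testing, including low readings in the control arm that need careful reading.

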2. OBJECTIVES

The primary objective of this study is to assess the effectiveness of the topically applied Timoptic-XE® or timolol (a non-selective beta adrenergic receptor antagonist) versus standard of care for the treatment of non-healing diabetic foot ulcers. The primary endpoint will be the measurement of the complete ulcer closure (as defined by “skin re-epithelialization without drainage or dressing requirements) at 12 weeks. The secondary outcomes will be the following: comparison of percent difference change in size from the randomization visit to the endpoint visit (post 12 weeks) between the treatment and control group, the time to wound closure between the two groups, and wound healing rates with impact of wound size between the treatment groups and measure quality of life using VR-36 Health Survey and the Lower Extremity Functional Scale Outcome Questionnaire.

The secondary objective of study is to profile the safety of topically applied Timoptic-XE® in the treatment of DFU. We will monitor serum levels of timolol post-application to determine the plasma concentration of timolol in relation to its systemic bioavailability. Timolol levels will be determined using reversed-phase ultraperformance liquid chromatography and UV detection.

Safety endpoint will be the measurement of all the adverse events associated with the use of Timoptic-XE®.

A tertiary/ancillary objective of the study is to compare efficacy of both arms of this study, Group A (SOC + Timoptic XE) and Group B (SOC + non-biologically active gel), to a “**Real-world cohort**” – patients who are not randomized and continue to receive care for their diabetic foot ulcer(s) not within the context of this research study. Passive follow-up these screen-failed patients via CPRS will be limited to charts related to the care of their foot ulcer(s).

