5. ADVERSE EVENTS

All adverse events reported spontaneously by the subject/or in response to questioning or observation by the investigator will be recorded.

Reporting of Adverse Events:

The Investigator will be responsible for assessing the relationship of the adverse event to the investigational product, and the seriousness and expectedness of the adverse event at the time of occurrence. All adverse events that occur during the trial will be documented.

AE's/SAE's reported during the study, or SAE's reported within 30 days of the end of the study, should be followed to resolution of the AE/SAE or, within thirty days from the end of the study, a further and final assessment of the outcome should be made. Each AE will be categorized as "serious" or "not serious" based on the definition of an SAE. An SAE is defined as an AE resulting in at least one of the outcomes described in the sections below.

The severity of AEs will be classified as "mild", "moderate", or "severe", based on the following definitions:

- Mild: Awareness of sign, symptom, or event, but easily tolerated; does not interfere with usual daily activities or tasks.
- Moderate: Discomfort enough to cause interference with usual daily activity; may warrant therapeutic intervention.
- Severe: Incapacitating; inability to perform usual activities and daily tasks; significantly affects clinical status; requires therapeutic intervention.

Adverse events will be assigned a relationship (causality) to the study products. The Investigator will be responsible for determining the relationship between an AE and the study product. The

type of event, organ system affected, and timing of onset of the event will be factors in assessing the likelihood that an AE is related to the treatment. Relationship of AEs to study products will be classified as follows:

- Not Related: No relationship exists between the AE and the treatment. The event is attributed to a pre-existing medical condition or an intercurrent event unrelated to the study product.
- Possibly Related: Follows the treatment, but may have developed as a result of an underlying clinical condition or treatments/interventions unrelated to the study product.
- Probably Related: Follows the treatment, but is unlikely to have developed as a result of the subject's underlying clinical condition or other treatment or other interventions.

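### The adverse-event outcome is defined by attribution to timolol, with no causality cut-off, and does not match the all-event recording and by-treatment analysis planned elsewhere

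*Combined protocol and SAP*

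**What the plan says.** Three places define the adverse-event outcome, each by reference to the active product:

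- Protocol Summary, Safety Endpoint, third secondary safety outcome: "Adverse events associated with the use of timolol".
- Protocol Summary, Study Objectives, among the secondary safety outcomes: "the measurement of all the adverse events associated with the use of Timoptic-XE".
- Section 2, Objectives: "Safety endpoint will be the measurement of all the adverse events associated with the use of Timoptic-XE".

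Section 5 sets a wider scope for data collection: "All adverse events reported spontaneously by the subject/or in response to questioning or observation by the investigator will be recorded", and "All adverse events that occur during the trial will be documented". It then provides a causality scale with five categories (not, possibly, probably or definitely related, and unknown), rated against the study products: "The Investigator will be responsible for determining the relationship between an AE and the study product".

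The analysis text, in the Protocol Summary (Data Analysis) and again in Section 6 (Analyses), plans logistic regression of the occurrence of each type of adverse event on treatment, adjusted for listed covariates. It does not restrict this to related events. The Clinical Outcomes list in Section 6 has an item counting adverse effects, also without reference to timolol.

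**The concern.** A blinded placebo arm allows the drug's effect on adverse events to be read from the difference in all events between arms, without anyone judging cause. An outcome limited to events associated with timolol puts a judgement in front of that comparison. The only means the protocol gives for making it is the investigator's rating, and the cut-off on that scale is not stated. Two analysts could count different events, particularly those rated possibly related or unknown.

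The secondary objective is to profile safety. A report that followed the three definitions faithfully could show attributed events only. Drug effects that resemble the background illness of patients with diabetes, such as fatigue or dizziness, are the ones most easily rated unrelated and so left out.

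**Working it through.** **1. The texts side by side.**

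| Element | Where | Restricted by causality? |
|---|---|---|
| Outcome definition | Protocol Summary (two places), Section 2 | Yes, with no cut-off |
| Recording | Section 5; every visit in the Study Flow Chart | No |
| Count of adverse effects | Section 6, Clinical Outcomes | No |
| Regression of each event type on treatment | Protocol Summary, Data Analysis; Section 6, Analyses | No |

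The definition is the only filtered element. It matches neither the data collected nor the analysis planned.

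**2. Check of the calculation against the plan's own figure.** The only powered comparison is for efficacy: 20% against 63% healed, 24 per arm, two-sided Fisher's exact test at 5%, 80% power. The exact rejection probability is the sum of Bin(i; 24, p_C) × Bin(j; 24, p_T) over all outcome pairs (i, j) whose Fisher p-value is at most 0.05. With p_C = 0.20 and p_T = 0.63 it is 82.5% at 24 per arm and 79.5% at 23. The stated 24 reproduces. This checks the method only; no adverse-event comparison is powered.

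**3. Illustration of what filtering does.** The documents give neither event rates nor attribution rates, so all rates here are assumptions. Let p be the proportion of subjects with an event and q the probability that the event is judged related. The proportion counted is then p × q in each arm, with 24 per arm.

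*True difference, 30% control and 60% timolol, equal attribution in both arms:*

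| q | Proportions counted | Power |
|---|---|---|
| 1 (all events) | 30% v 60% | 47% |
| 0.75 | 22.5% v 45% | 28% |
| 0.50 | 15% v 30% | 16% |
| 0.25 | 7.5% v 15% | 6% |

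*No true difference, 30% in both arms:*

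| q control / q timolol | Proportions counted | False-positive rate |
|---|---|---|
| 1 / 1 (all events) | 30% v 30% | 2.6% |
| 0.50 / 0.50 | 15% v 15% | 2.4% |
| 0.25 / 0.50 | 7.5% v 15% | 6.4% |

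Equal attribution in the two arms leaves the false-positive rate essentially unchanged and costs power. Bias needs attribution that differs by arm.

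**4. Could attribution differ by arm?** Supplies are repackaged in identical coded dispensers (Section 4.2), which argues against it. Against that, timolol levels are measured at weeks 4, 8 and 12 and acted on for individual patients (Section 4.3.3), and the documents do not say whether the results are kept from the person rating causality. Differential attribution is possible but not shown.

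**The case against.** A reader might infer that the outcome has no meaning in the placebo arm, that placebo subjects score zero by definition, and that the safety comparison has no valid control. The documents do not support this. All events are recorded at every visit in both arms. Causality is rated against the study products, so a blinded investigator can rate an event in either arm. The planned regression on treatment is itself a controlled comparison with no causality filter, and the zero-events reading would leave it nothing to compare. It can also be argued that *associated with* means the statistical association which that regression estimates, since no sentence says the outcome will be filtered by the rating.

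Three further points limit the concern:

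- Heart rate and blood pressure changes are separate secondary safety outcomes that need no causality judgement, so a slow pulse would not disappear from the safety results.
- Any figure for the share of events lost only restates the share assumed to be rated unrelated.
- A reader might see a contradiction in Section 2 naming adverse events as the safety endpoint while the Protocol Summary makes serum timolol the primary safety outcome. Section 2 gives no ranking and also mentions serum monitoring, so this is an unstated hierarchy and at most a point to clarify.

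These arguments defeat the strong reading. They do not settle the wording: three definitions name only the active product, no cut-off is given, and the definition differs from what is recorded and analysed.

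**Conclusion.** The point holds as a mismatch between the outcome's definition and the plan's own recording and analysis, with a causality filter left unspecified. A control comparison exists. If the outcome were reported as defined, it would be less sensitive than a comparison of all events by arm, and it could be biased if attribution differed between arms.

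The size cannot be derived from the documents. The fall in power from 47% to between 28% and 6% rests on assumed event rates of 30% and 60%, equal attribution of 75% down to 25%, and attribution treated as one probability per affected subject. The 6.4% false-positive rate rests on assumed attribution of 25% and 50%. These figures show direction and mechanism and are not forecasts. For a secondary outcome with the data already collected, this is an inexpensive improvement worth making, and it does not call the trial's design into question.

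**What to change.** In the Protocol Summary (Study Objectives and Safety Endpoint) and in Section 2, define the outcome as all adverse events with onset after first application, by randomised arm and regardless of causality rating. This agrees with the recording in Section 5 and the regression in the Protocol Summary and Section 6. The onset limit is needed because the Study Flow Chart records events from the first screening visit.

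Add a supportive table of related events for both arms. State which of the five categories count as related, and say explicitly where *unknown* goes.

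The change is one of wording and table specification, with no new data collection. The cost is longer event tables.
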